5.3 Participant Selection

Inclusion Criteria:

- Children previously recruited to the DRIFT trial
- Parents/carers are willing and able to give informed consent and children willing to assent to participation in the study.

Exclusion Criteria

• Children with metal implants that are incompatible in MRI scanners will be excluded from the neuroimaging element of the study.

6. ASSESSMENTS

All assessments will be adapted to the child's abilities.

6.1 Cognitive Assessments

Assessment will be undertaken by child psychologists.

Cognitive testing in this group of children needs to use a method with a wide spread of abilities as some of the study children have very significant disabilities (Cognitive score below 55). The British Ability Scales (BAS III) comprise 21 short tests, each measuring particular types of knowledge, thinking and/or skills (Elliott and Smith. GL Assessment; London. 2012). The final type of score is "age equivalent". This is the age at which the score achieved by the child was average. The BAS III has a basal threshold at a developmental age of 3 years. In the event that children do not attain the basal scoring threshold of the BAS III, the cognitive and language scales from the Bayley Scales of Infant and Toddler Development III (BSID III) (Bayley N. Harcourt Assessment: San Antonio; 2006) will be administered. This test also yields Developmental Age Equivalent score from 1 month to 3 years. In order to compare scores in all children, developmental age scores will be converted into a developmental quotient score: [developmental age equivalent score \div biological age at assessment x 100] for each child. This allows severely delayed children to have a cognitive score rather than being labelled as "untestable".[14] The final cognitive score for children of all abilities will therefore be a cognitive developmental quotient and a continuous variable.

The BAS_III and BSID III will be adapted for use in Polish speaking children.

The individual scales for BASIII are:

- Block building
- Copying
- Early number concepts
- Matching letter-like forms
- Matrices
- Naming Vocabulary
- Number Skills
- Pattern Construction
- Picture Construction
- Picture Similarities
- Quantitative Reasoning
- Recall of Designs
- Recall of Digits Backwards
- Recall of objects

- Recognition of pictures
- Speed of information processing
- Spelling
- Verbal Comprehension
- Verbal Similarities
- Word definitions
- Word reading

The individual scales for BSID III are:

- Cognitive Scale
- Language Scale (receptive and expressive language)

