5.2 Statistical Considerations

In total 74 children (54 from Bristol and 20 from Poland) were randomised to the DRIFT trial of which 66 survived. 16 children are available for assessment in Poland and 50 in Bristol. Based on a similar effect size documented with severe cognitive disability at 2 years of age a two group continuity corrected chi-square test with a 5% two-sided significance level will have 80% power to detect the difference in severe cognitive disability between a control group proportion of 59% and odds ratio of 0.17 (i.e. an intervention proportion of 19.7%) when the sample size in each group is 28. With 60 infants (30 in each group) we will have 97% power (with an alpha of 5%) to detect a mean cognitive difference of 1 standard deviation (commonly 15 points) between the DRIFT and control groups.

45 UK children will be assessed in Bristol, and 15 Polish children in Katowice, Poland, assuming a 90% follow-up rate. It is intended to recruit 45 Children (22 DRIFT, 23 Control) from the Bristol cohort and 15 (8 DRIFT, 7 Control) from the Poland cohort.

Funding is available for the study to be completed in the UK and in Poland. **This protocol describes the UK cohort only**. The Poland cohort will be completed under a separate protocol and in accordance with local governance and regulatory requirements.

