7.4 Data Analysis

Analysis will be performed by intention to treat and hence primary outcome (cognitive score) will be assessed by comparing mean scores, and analysed using the Student t-test (unpaired). Developmental Quotient derived from age equivalent cognitive scores will be used as a continuous variable, derived from either the BAS III or BSID Bayley III scales.

For the secondary outcomes with continuous outcomes (eg Movement ABC), these will also be analysed using Students t-test, unless found in this population to not follow a normal distribution, in which case either a suitable transformations will be sought or a non-parametric approach considered.

For the binary secondary outcomes (eg functional motor impairment, Strengths and Difficulties, use of specialised health, rehabilitative or educational services) the Chi-Square or 2-tailed Fishers exact test will be used. Output from the clinical neuroimaging will be transformed into either binary (in the case of radiology reports) or continuous data (in the case of quantitative measures) and analysed as above.

Any sensitivity analyses will be performed using multivariate linear regression analysis to control for variables of interest. Co-variate variable selection will be performed a-priori for the models, and included if clinically felt to represent potentially important cofounders. To provide consistent reporting, it is anticipated that at least one sensitivity analysis will be performed: adjusting for the pre-randomisation co-variates used in the initial DRIFT trial report.

For all tests a conventional level of statistical significance at 5% will be used.

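### The primary t-test has no site term, although the stated power needs Bristol and Katowice combined and the Polish children take adapted instruments; a site difference would cost power

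*Protocol*

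**What the plan says.** Protocol section 7.4 names the primary test: the "primary outcome (cognitive score) will be assessed by comparing mean scores, and analysed using the Student t-test (unpaired"). It adds that "Developmental Quotient derived from age equivalent cognitive scores will be used as a continuous variable". It mentions no site term and no stratification. The one covariate-adjusted analysis it anticipates is a sensitivity regression on the pre-randomisation covariates of the first trial report, which it does not list.

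Section 5.2 justifies the size of the comparison: "With 60 infants (30 in each group) we will have 97% power (with an alpha of 5%) to detect a mean cognitive difference of 1" SD, which it puts at 15 points in the usual case. The 60 are made up across countries: "45 UK children will be assessed in Bristol, and 15 Polish children in Katowice, Poland". The planned split is 22 DRIFT and 23 control in Bristol, and 8 DRIFT and 7 control in Katowice. The same section then limits the protocol's scope to the UK children and places the Polish cohort under a separate protocol.

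Section 6.1 builds the quotient from age-equivalent scores and states that "The BAS_III and BSID III will be adapted for use in Polish speaking children". It does not mention Polish norms, equating or validation.

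**The concern.** An age equivalent is read off the test's own reference data. If the instrument is adapted for another language, the same quotient need not mean the same ability. Several of the listed scales depend heavily on language (spelling, word reading, word definitions, verbal similarities, naming vocabulary), as does the language scale of the Bayley fallback. The two groups of children may also differ for reasons unrelated to the instrument. Either way, the mean quotient could differ between Bristol and Katowice.

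A t-test without a site term counts such a difference as noise. Precision lost this way cannot be recovered by recruiting more children, because the cohort is closed: section 5.2 gives 66 survivors. What is at stake is a real treatment effect missed because the analysis ignores a variable known for every child.

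**Working it through.** **Inputs from the protocol.** Sections 5.2 and 7.4: 30 per arm, SD 15 points, difference 1 SD, alpha 5% (taken as two-sided), site split 22/23 and 8/7, unpaired t-test.

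**Assumptions.** The site difference, written d in SD units, is not in the documents; 0.5, 1 and 1.5 SD in either direction are used as a range. A true effect of 0.6 SD is a second assumption, used to show what happens if the effect is smaller than planned.

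**Step 1: reproduce the stated power.** The noncentrality is 1/√(1/30 + 1/30) = 3.87. With 58 df the noncentral t gives 96.8% (97.2% by the normal approximation), which matches the stated 97%. Bristol alone, with 22 v 23, gives 90.6% (91.8% normal). The stated figure therefore assumes that both sites enter one comparison.

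**Step 2: where a site difference goes.** Polish children are 8/30 of the DRIFT arm and 7/30 of the control arm.
- Into the estimate: (8/30 − 7/30)d = d/30, which is 0.5 points for a 15-point difference.
- Into the residual sum of squares: (8×22/30 + 7×23/30)d² = 11.23d², in units of the within-site variance. The expected pooled variance is therefore multiplied by 1 + 11.23d²/58 = 1 + 0.194d².

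With the split held fixed, the true standard error of the difference does not change, but the t-test's estimate of it is inflated by about √(1 + 0.194d²): 1.02, 1.09 and 1.20 at d = 0.5, 1 and 1.5. That is why the test is conservative.

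**Step 3: operating characteristics of the unadjusted test.** The numerator is normal with mean (effect + d/30)/√(2/30). The variance estimate is a noncentral chi-square with 58 df and noncentrality 11.23d², divided by 58. Integrating over it gives the table below, and simulation with the same fixed split agrees. The lower power applies when Polish scores run lower, the higher when they run higher.

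| Site difference | Type I error | Power, 1 SD effect | Power, 0.6 SD effect |
|---|---|---|---|
| 0 | 5.0% | 96.8% | 62.8% |
| 0.5 SD | 4.5% | 95.9% to 96.9% | 58.5% to 63.4% |
| 1 SD | 3.4% | 93.8% to 96.3% | 50.7% to 60.6% |
| 1.5 SD | 2.2% | 89.7% to 95.0% | 40.0% to 55.0% |

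**Step 4: the same data with a site term.** The information for the arm effect is 22×23/45 + 8×7/15 = 14.98, against 15 for the unstratified comparison. With 57 df, power is 96.7% for a 1 SD effect and 62.7% for 0.6 SD, and type I error is 5%, whatever the additive site difference.

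**The case against.** The strongest reply is that an unadjusted t-test on a randomised comparison is valid and that centre adjustment is often left to the statistical analysis plan, which is not shown. At the protocol's own 1 SD effect the loss is small unless the site difference exceeds about 1 SD, and the larger losses need a smaller effect that the protocol does not name. All of this stands. It makes the point one of efficiency. It does not remove it, because section 7.4 names a specific test and a better one is available at almost no cost.

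Section 5.2 also limits the protocol to the UK cohort, and section 7.4 never says in words that the sites are pooled. Pooling is an inference from the 60 children and the 97%. It is a sound inference, but the two statements need reconciling. That the Polish versions are translated is likewise an inference; the text speaks only of adaptation.

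The sensitivity regression may already contain centre. Its covariates are not listed, so a reader should not conclude that site is left out. Even if it is included, the primary test remains unadjusted.

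Two stronger readings are tempting. One is that a positive pooled result could not be told apart from an instrument difference. The planned split does not support this: only 1/30 of any site difference reaches the estimate, and type I error falls. The other is that a fixed cut-off for severe disability would mean different abilities in the two countries. The protocol states no school-age cut-off on the quotient, so there is nothing to test that against.

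**Conclusion.** The point holds as an avoidable loss of power in the primary comparison. The plan relies on both sites for its power, has adapted instruments at one of them, and names a test that treats any mean difference between sites as error. The consequence is a conservative test; a significant result is not undermined by it. For the planned effect the loss is about 3 percentage points at worst at a 1 SD site difference, and about 7 at 1.5 SD. If the true effect is 0.6 SD, the corresponding losses are about 12 and 23 points.

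These figures rest on an assumed additive site difference, equal within-site SDs and the planned split of 22/23 and 8/7. If the children who attend are less evenly split by arm within site, more of the difference enters the estimate.

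**What to change.** In section 7.4, make the primary analysis a linear model of the developmental quotient on treatment arm and site. For severe cognitive disability, use a comparison stratified by site (Mantel-Haenszel). Show the Bristol-only estimate beside the combined one as a supportive result on the unadapted instruments. In section 5.2, state that the primary analysis combines the two cohorts, and reconcile this with the sentence limiting the protocol to the UK. Make the change before any unblinded analysis.

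The cost is one degree of freedom (96.8% to 96.7% power when there is no site difference) and no new data, since site is known for every child. A site term removes an additive offset only. It does not correct a difference in scale between the adapted and unadapted versions, which is one reason to show the Bristol-only estimate.

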6.2 Assessment of Visual Function

Children will be assessed by trained vision specialists. Analysis of all visual data will be undertaken by [name].

The UK visual assessments will comprise:

A standard protocol to explore a range of visual and visual cognitive functions, for all of which age and developmental normative data are available.

The general approach will be to obtain some information relating to a wide range of visual functions relating to:

- How well child can discriminate small objects
- How well child can move their eyes
- How well child can interpret and use visual information
- Focussing power of the eye
- Anatomical structure of the retinal and optic nerve

Specific tests:

- (1) History relating to visual behaviour :
- (2) CVI inventory (51 Q version, including 12 Q mini-version used previously [9])
 [15]
- (3) Direct observations:
 - Binocular and Monocular visual acuity: we will use Crowded LogMar, with matching card if needed, where possible or Cardiff Cards if not; +/- pinhole to approximate for "best corrected"
 - o Binocular and monocular Contrast sensitivity (Cardiff contrast cards)
 - o Stereopsis using the "Preschool" Randot test
 - Motor and Sensory Fusion
 - Ocular Alignment (Cover tests alternate cover tests)

- Ability to fix and follow a target –monocularly and binocularly (toy, lit-toy or noisy lit toy)
- Ability to shift attention to a competing object within the visual field (toy, lit toy or noisy lit toy)
- Pursuit eye movements horizontally and vertically, fast and slow
- o Saccadic eye movements horizontally and vertically, fast and slow
- Full-field optokinetic nystagmus (OKN)
- Vestibulo-ocular reflex nystagmus (postrotational)
- Accommodation to a lit target (RAF rule) and dynamic retinoscopy
- Visual fields to confrontation
- Tests of visuoperceptual skills:
 - Post-box
 - Rectangles
 - Biological motion and form –in-motion (on a laptop or tablet)
 - Contour integration
 - Familiar pictures in unfamiliar aspects (on a laptop or tablet)

Finally anaesthetic (proxymotocaine 0.5%), then cycloplegic drops will be instilled and the child's refractive error measured by a Canon R50 autorefractor, unless these data are available from tests no more than 6 months previously.

A photograph (with/without drops) will be taken of each eye using a Topcon PR2000 non-mydriatic camera to document fundus appearance and allow analysis of optic nerve characteristics

It is estimated this will take up to 60 minutes per child (40 if no drops used, 60 if drops needed)

In Poland visual acuity results (with details of test used), motility, cover test and refraction results can be collected locally or obtained from existing records. The question battery will be sent for completion by the mother/carer.

Visual outcomes:

(i) Severe visual impairment will be defined according to WHO taxonomy: Blind - 3/60 or worse; Low vision =3/60 to 6/18

(ii) Additional functional impairment will be defined as significant field defect (e.g. hemianopia), nystagmus in primary position and/or contrast sensitivity below age-matched or developmental age-matched norms

(iii) Mild impairments will include strabismus, best binocular acuity < 6/6 and/or unilateral amblyopia (difference between eyes of 2 lines or more LogMAR or behavioural equivalent).

(iv) Significant refractive error will be defined as spherical equivalent (SE) > +2 or < -1 or >:1 D anisometropia or >1D astigmatism.

(v) CVI will be indicated by performance in perceptual test (postbox, rectangles, contours) worse than that of 95% of age-matched or developmental age-matched children with no known developmental problems and/or higher symptom score on question battery than population-based control sample [9].

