Prematurely-born children have a higher prevalence of visual defects than do children born at term [5] and in particular the spectrum of vision problems known collectively as "cerebral visual impairment" (CVI) is a recognised complication of preterm brain injury, particularly if involving the periventricular white matter [6]. Visual functions correlate with neurodevelopmental outcome and brain volume in preterm infants [7]. Severe CVI is the leading cause for children being registered as blind in the UK [8] and developed world and may additionally be associated with ocular, optic nerve or refractive problems which cause further impairment. Less severe CVI can involve damage to visual skills which have an important effect on school performance and tasks of everyday life [9]. Clinical assessment of CVI is difficult before the age of 5 years, however a recent study found evidence of CVI in 89% of children with known central nervous system damage [10] thus it is important to assess this area of function to fully understand the impact of severe IVH, PHVD and/or the impact of DRIFT.

Every preterm infant with severe cerebral palsy or severe cognitive or visual impairment will require lifelong parental and social care. The cost to society due to the complications of prematurity is significant. Based on 2003 US figures [11] the estimated lifetime costs per infant with cerebral palsy, severe cognitive impairment and blindness is £614,000, £675,000 and £400,000 respectively. Data from the UK EPICure study indicate that by age 11 the annual health and social service costs of children with serious neurodevelopmental disability are almost double those of children without disability (£1,225 vs £695) [12]. This adds a significant additional economic burden on the NHS and social care.

As cognitive testing at 2 years is limited and can be difficult in children with motor impairment, it is important to do more comprehensive testing at school age. Cerebral visual impairment concerns more complicated aspects of vision than just visual acuity or strabismus and cannot be adequately tested at 2 years. Thus it is important to thoroughly assess vision including techniques that can detect and define cerebral visual impairment. The MR imaging performed at term showed cerebral lesions and/or impaired brain growth in a large proportion of the infants.

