4.2 Secondary Outcomes

- Cerebral visual function
- Sensorimotor disability
- Functional status
- Emotional/behavioural function
- Preference based measures of health related quality of life
- Costs of initial hospitalisation and treatment during the neonatal period (including emergency transportation, periods of intensive care, and readmissions based on hospital records in the UK cohort)
- Costs of subsequent health care in childhood (based on hospital records from the UK cohort)
- Health and social care costs and impact on family at age 11 (based on parent recall)

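### Section 6.2 defines cerebral vision, the first-listed secondary outcome, only as a yes/no CVI label although graded scores are collected; naming a score would recover a useful amount of power

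*Protocol*

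**What the plan says.** - Protocol section 4.2 lists "Cerebral visual function" first among the secondary outcomes, without an analysis variable. Section 4 makes improvement in cerebral visual dysfunction secondary hypothesis (a).
- Section 6.2 collects graded material for UK children: a 51-question CVI inventory and several visuoperceptual tests. It says of the visual functions explored: "for all of which age and developmental normative data are available".
- Under its visual outcomes heading, section 6.2 lists five items, all of them categories. The only one for cerebral vision is item (v), whose first route is: "CVI will be indicated by performance in perceptual test (postbox, rectangles, contours) worse than that of 95% of age-matched". The comparison group may instead be chosen by level of development: "or developmental age-matched children with no known developmental problems". A second route, which can stand alone or be combined with the first, rests on the questionnaire: "and/or higher symptom score on question battery than population-based control sample". No cut-off is given for the symptom score.
- For Poland, section 6.2 lists no perceptual tests, but says: "The question battery will be sent for completion by the mother/carer". Section 5.2 states that this document covers the UK cohort and that Poland runs under a separate protocol.
- Section 7.4 says of binary secondary outcomes that "the Chi-Square or 2-tailed Fishers exact test will be used". Continuous ones get a t-test, a transformation or a non-parametric method. No visual outcome is named as an example of either kind.
- Section 3.1.2 gives a CVI rate as background: "a recent study found evidence of CVI in 89% of children with known central nervous system damage".

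**The concern.** The label cuts graded measurements at the edge of normal performance. A child who moves from very poor to moderately poor visual perception stays CVI-positive and counts as unchanged. In a cohort selected for serious brain injury, many children in both arms may lie on the same side of the cut.

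The protocol argues the other way for cognition in the same children. Section 6.1 chooses a continuous developmental quotient so that severely delayed children still receive a score, and section 7.4 compares mean scores. No reason is given for treating cerebral vision differently.

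With about 60 children and no possibility of enrolling more, a null comparison of CVI percentages could be read as no visual benefit of DRIFT, although scores already in the database might show one.

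**Working it through.** **Inputs from the protocol.** Two-sided 5% tests; 30 per arm over both sites; 23 control and 22 DRIFT children in the UK (section 5.2); 89% CVI in another group (section 3.1.2).

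**Assumed, because not given.** The control-arm CVI rate p0 (50 to 89%) and the shift d in the underlying score (0.3 to 1.2 SD). The 1 SD shift is the one that section 5.2 uses for cognition.

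**The protocol's own figures first.** They concern cognition; none is stated for vision.
- 59% with an odds ratio of 0.17 gives 19.7%. The continuity-corrected formula gives n = 27.8, so 28 per group, as stated.
- A 1 SD difference with 30 per group has 96.8% power by the noncentral t, matching the stated 97%.

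**Model for vision.** One normally distributed score, with the CVI label as a threshold on it.
- DRIFT rate: p1 = Φ(Φ⁻¹(p0) − d). For p0 = 0.89 and d = 0.8: Φ(1.2265 − 0.8) = 66.5%.
- Score: noncentral t with noncentrality d·√(n0·n1/(n0+n1)). For 30/30 and d = 0.8: 0.8 × √15 = 3.10, power 86.1%.
- Label: full enumeration of the two binomials, with uncorrected chi-square and Fisher's exact test.

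**Control rate 89%, power in %:**

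| Arms | d | DRIFT rate | Score | Chi-square | Fisher | Loss, chi-square / Fisher |
|---|---|---|---|---|---|---|
| 30/30 | 0.3 | 82.3 | 20.8 | 11.7 | 4.8 | 9 / 16 |
| 30/30 | 0.5 | 76.6 | 47.8 | 24.4 | 14.3 | 23 / 34 |
| 30/30 | 0.75 | 68.3 | 81.5 | 50.6 | 38.5 | 31 / 43 |
| 30/30 | 0.8 | 66.5 | 86.1 | 56.6 | 44.6 | 30 / 42 |
| 30/30 | 1.0 | 59.0 | 96.8 | 78.4 | 69.3 | 18 / 28 |
| 30/30 | 1.2 | 51.1 | 99.5 | 92.2 | 87.5 | 7 / 12 |
| 23/22 | 0.5 | 76.6 | 37.4 | 18.3 | 17.9 | 19 / 20 |
| 23/22 | 0.8 | 66.5 | 74.6 | 44.3 | 42.8 | 30 / 32 |
| 23/22 | 1.0 | 59.0 | 90.6 | 66.0 | 63.1 | 25 / 28 |

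**Lower control rates, 30 per arm, d = 0.8.** The score has 86.1% power throughout.

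| Control rate | Chi-square | Loss | Fisher | Loss |
|---|---|---|---|---|
| 50% | 65.1 | 21 | 55.2 | 31 |
| 60% | 68.6 | 17 to 18 | 58.6 | 27 to 28 |
| 70% | 68.8 | 17 | 58.8 | 27 |

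Most of the loss at 0.8 SD therefore comes from dichotomising. A rate near 89% raises the chi-square loss from 17 to 21 points to about 30.

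**The case against.** **The protocol does not confine the comparison to the label.** A reader might infer that it does. Item (v) can be read as a case definition, section 7.4 names no visual outcome, and its continuous rule is open to the visual scores. A statistical analysis plan, not at hand, may use it. This stands. What remains is that 6.2 sets out the visual outcomes and names no continuous one.

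**The 89% is not a DRIFT rate.** A reader might infer that the protocol's own figure puts this outcome at its ceiling. It does not. The figure comes from other children, under a definition of CVI not given here, and is offered as a reason for assessing CVI. Matching on developmental age, which item (v) allows, could lower the rate in this cohort; the and/or rule could raise it. This stands too, but the loss at control rates of 50 to 70% does not depend on it.

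**The upper figures lean on Fisher's test.** At 30 per arm and 89%, the smallest expected count at 0.5 SD is 30 × (1 − (0.89 + 0.766)/2) = 5.2, so chi-square would be the usual choice. That is fair for the full cohort. The perceptual tests are described for the UK, where the same count is 22 × 0.172 = 3.8, and there the two tests differ little.

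**The score benchmark is optimistic.** It assumes one normal score that every child can complete, whereas the real rule joins several tests and a questionnaire. Section 3.1.2 reports that 9% had no useful vision at 2 years, so floor effects and untestable children are likely and would shrink the gain.

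**CVI as a diagnosis is easy to interpret.** True, and a reason to keep reporting it.

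**Conclusion.** The point holds as a conditional loss of power from naming only a label for cerebral vision when graded scores are available.

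- Under a normal score and two-sided 5% tests, with 30 per arm and a 0.8 SD shift, the loss is about 17 to 21 points by chi-square for control rates of 50 to 70%.
- If the control rate were near 89%, it is about 18 to 31 points by chi-square, or 28 to 43 by Fisher, for shifts of 0.5 to 1 SD.
- For the UK cohort at 89% and 0.8 SD, power is 44% (chi-square) or 43% (Fisher) against 75% for the score.
- At 89% and 30 per arm, the loss falls to 9 to 16 points at 0.3 SD and 7 to 12 at 1.2 SD.

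The control rate and the visual effect size are assumptions throughout. The documents do not support a firm statement that the comparison will lose 20 to 40 points, or that the DRIFT children sit at a ceiling. This is a secondary outcome with no stated power, so nothing in the sample size justification is affected.

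**What to change.** In sections 6.2 and 7.4:

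1. Name the CVI inventory symptom score as the between-arm comparison of cerebral visual function, analysed under the existing rule for continuous outcomes.
2. Name the UK perceptual test scores as supporting comparisons under the same rule. Where children who cannot perform a test are given the worst rank, use a rank test only; a t-test does not fit that scoring.
3. Add Polish inventory scores only if the separate Polish protocol collects the same instrument.
4. Keep the CVI label and report its count and percentage per arm beside the score.

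The cost is wording: no new children, visits or tests. The downside is that a difference in scores or ranks is harder to read clinically than a percentage, which is why the percentage stays in the report.
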